9.4.7. Uveitis Evaluation

At each study visit, the investigator will ask the participant/caregiver whether they developed uveitis since the last visit and evaluate the participant for any symptoms of acute anterior uveitis since the last visit as specified in the Schedule of Activities (Section

2). If the participant has no prior ophthalmologist-diagnosed uveitis and develops eye pain or discomfort, eye redness, blurring of vision, or any other symptoms suggestive of acute anterior uveitis, the participant must be evaluated by an ophthalmologist. It is expected that all children with JIA will be on screening and regular evaluation with ophthalmologists based on local/regional/national guidelines.

9.4.8. Children's Depression Inventory 2 Short Form (CDI-2)

The Children's Depression Inventory-2 (CDI-2) short form is modeled after the Beck Depression Inventory and is a 12-item self-reported scale designed to measure depressive symptoms in children and adolescents (ages 7 years and older) (Helsel and Matson 1984; Kovacs 1992; Ahlen and Ghaderi 2017). The instrument has a recall period of the past 2 weeks and responses use a 3- item Likert scale. A higher score indicates more clinically severe depression.

9.4.9. Columbia–Suicide Severity Rating Scale (C-SSRS)

The C-SSRS is a scale that captures the occurrence, severity, and frequency of suicidal ideation and behavior during the assessment period via a questionnaire. The scale was developed by the National Institute of Mental Health (NIMH) trial group Treatment of Adolescent Suicide Attempters (TASA) for the purpose of being counterpart to the Columbia Classification Algorithm of Suicide Assessment (C-CASA) categorization of suicidal events and is administered by the clinician.

The instrument is validated for use in children ages 7 to 11 (using the Children C-SSRS) as well as adults ages 12 and older (using the Adult C-SSRS form). The instrument is a composite instrument with responses being a mixture of Yes/No, ordinal and nominal scales. Higher scores indicate higher suicidal ideation and behavior.

The sites will use the appropriate version according to the age. Respondents will continue with the version of the instrument they begin the study with even if their age changes during the course of the study.

9.4.10. Self-Harm Supplement Form

The Self-Harm Supplement Form is part of the C-SSRS instrument. It consists of 1 question and is completed at any visit, including baseline visits by the clinician. The question asks for the number of suicidal or non-suicidal self-injurious behaviors the participant experienced since last assessment.

For each unique event identified, a questionnaire (Self-Harm Follow-Up Form), which collects supplemental information on the self-injurious behavior, must be completed. This information is then documented in the eCRF.

9.4.11. Safety Monitoring

Lilly will periodically review evolving aggregate safety data within the study by appropriate methods.

Refer to Interim Analyses Section 10.3.8) for information about additional analyses of the safety data.

9.4.11.1. Hepatic Safety Monitoring

Close hepatic monitoring^a

Laboratory tests (Appendix 4), including ALT, AST, ALP, TBL, direct bilirubin, gamma-glutamyl transferase (GGT), and creatine kinase (CK), should be repeated within 48 to 72 hours to confirm the abnormality and to determine if it is increasing or decreasing, if 1 or more of these conditions occur:

If a participant with baseline results of...	develops the following elevations:
ALT or AST $<1.5 \times$ ULN	ALT or AST $\geq 3 \times$ ULN
ALP $<1.5 \times$ ULN	ALP $\geq 2 \times$ ULN
TBL $<1.5 \times$ ULN	TBL $\geq 2 \times$ ULN, except for patients with Gilbert's syndrome
ALT or AST $\geq 1.5 \times$ ULN	ALT or AST $\geq 2 \times$ baseline
ALP $\geq 1.5 \times$ ULN	ALP $\geq 2 \times$ baseline
TBL $\geq 1.5 \times$ ULN	TBL $\geq 1.5 \times$ baseline, except for patients with Gilbert's syndrome

Abbreviations: ALP = alkaline phosphatase; ALT = alanine aminotransferase; AST = aspartate aminotransferase; TBL = total bilirubin; ULN = upper limit of normal.

^a All ULN values should be age adjusted (AAULN) for participants <18 years of age.

If the abnormality persists or worsens, clinical and laboratory monitoring, and evaluation for possible causes of abnormal liver tests should be initiated by the investigator in consultation with the Lilly-designated medical monitor. At a minimum, this evaluation should include physical examination and a thorough medical history, including symptoms, recent illnesses (for example, heart failure, systemic infection, hypotension, or seizures), recent travel, history of concomitant medications (including over-the-counter), herbal and dietary supplements, history of alcohol drinking, and other substance abuse.

Initially, monitoring of symptoms and hepatic biochemical tests should be done at a frequency of 1 to 3 times weekly, based on the participant's clinical condition and hepatic biochemical tests. Subsequently, the frequency of monitoring may be lowered to once every 1 to 2 weeks, if the participant's clinical condition and lab results stabilize.

Monitoring of ALT, AST, ALP, and TBL should continue until levels normalize or return to approximate baseline levels. Special care should be taken to minimize the volume of blood taken during hepatic monitoring.

Comprehensive hepatic evaluation

A comprehensive evaluation should be performed to search for possible causes of liver injury if 1 or more of these conditions occur:

If a participant with baseline results of...	develops the following elevations:
--	------------------------------------

ALT or AST $<1.5 \times$ ULN	ALT or AST $\geq 3 \times$ ULN with hepatic signs/symptoms ^b , or ALT or AST $\geq 5 \times$ ULN
ALP $<1.5 \times$ ULN	ALP $\geq 3 \times$ ULN
TBL $<1.5 \times$ ULN	TBL $\geq 2 \times$ ULN (except for participants with Gilbert's syndrome)
ALT or AST $\geq 1.5 \times$ ULN	ALT or AST $\geq 2 \times$ baseline with hepatic signs/symptoms ^b , or ALT or AST $\geq 3 \times$ baseline
ALP $\geq 1.5 \times$ ULN	ALP $\geq 2 \times$ baseline
TBL $\geq 1.5 \times$ ULN	TBL $\geq 1.5 \times$ baseline (except for participants with Gilbert's syndrome)

Abbreviations: ALP = alkaline phosphatase; ALT = alanine aminotransferase; AST = aspartate

aminotransferase; TBL = total bilirubin; ULN = upper limit of normal.

^a All ULN values should be age adjusted (AAULN) for participants <18 years of age.

^b Hepatic signs/symptoms are severe fatigue, nausea, vomiting, right upper quadrant abdominal pain, fever, rash, and/or eosinophilia $>5\%$.

At a minimum, this evaluation should include physical examination and a thorough medical history, as outlined above, as well as tests for PT-INR and direct bilirubin, if TBL was elevated, tests for viral hepatitis A, B, C, or E; tests for autoimmune hepatitis; and an abdominal imaging study (for example, ultrasound or computed tomography [CT] scan).

Based on the participant's age, medical history, and initial results, further testing should be considered in consultation with the Lilly-designated medical monitor, including tests for viral hepatitis A, B, C, E; autoimmune hepatitis; or an abdominal imaging study (for example, ultrasound, MRI, or CT scan). Consider additional tests, based on the medical history and clinical picture, including tests for hepatitis D virus, cytomegalovirus, Epstein-Barr virus, acetaminophen levels, acetaminophen protein adducts, urine toxicology screen, Wilson's disease, blood alcohol levels, urinary ethyl glucuronide, and blood phosphatidylethanol. Special care should be taken to prioritize more pertinent blood tests and minimize the volume of blood taken during hepatic evaluation. Based on the circumstances and the investigator's assessment of the participant's clinical condition, the investigator should consider referring the participant for a pediatric hepatologist or gastroenterologist consultation, magnetic resonance cholangiopancreatography, endoscopic retrograde cholangiopancreatography, cardiac echocardiogram, or a liver biopsy as deemed appropriate for the clinical condition and participant's age.

Additional hepatic data collection (hepatic safety CRF) in study participants who have abnormal liver tests during the study

Additional hepatic safety data collection in hepatic safety CRF should be performed in study participants who meet 1 or more of the following 5 conditions:^a

1. Elevation of serum ALT to $\geq 5 \times$ ULN on 2 or more consecutive blood tests (if baseline ALT $<1.5 \times$ ULN)
 - In participants with baseline ALT $\geq 1.5 \times$ ULN, the threshold is ALT $\geq 3 \times$ baseline on 2 or more consecutive tests

2. Elevated TBL to $\geq 2 \times$ ULN (if baseline TBL $< 1.5 \times$ ULN) (except for cases of known Gilbert's syndrome)
 - In participants with baseline TBL $\geq 1.5 \times$ ULN, the threshold should be TBL $\geq 2 \times$ baseline
3. Elevation of serum ALP to $\geq 2 \times$ ULN on 2 or more consecutive blood tests (if baseline ALP $< 1.5 \times$ ULN)
 - In participants with baseline ALP $\geq 1.5 \times$ ULN, the threshold is ALP $\geq 2 \times$ baseline on 2 or more consecutive blood tests
4. Hepatic event considered to be a SAE
5. Discontinuation of study drug due to a hepatic event

Note: the interval between the two consecutive blood tests should be at least 2 days.

^a All ULN values should be age adjusted

9.4.11.1. Hepatic Safety Data Collection

Additional safety data should be collected via the electronic data entry if 1 or more of the following conditions occur:

- elevation of serum ALT to $\geq 5 \times$ ULN on 2 or more consecutive blood tests,
- elevated serum TBL to $\geq 2 \times$ ULN (except for cases of known Gilbert's syndrome),
- elevation of serum ALP to $\geq 2 \times$ ULN on 2 or more consecutive blood tests,
- participant discontinued from treatment due to a hepatic event or abnormality of liver tests, or
- hepatic event considered to be an SAE.

9.4.11.2. Hepatitis B Monitoring

Participants who are HBsAg- and HBcAb+ at screening, regardless of other hepatitis B testing results, will have a plasma HBV DNA specimen obtained to be analyzed by the central laboratory. Such participants who are determined to be HBV DNA negative (undetectable) may be enrolled into the study with required HBV DNA monitoring every 3 to 4 months during treatment and 12 weeks after the last dose of ixekizumab.

Participants who are found to be HBV DNA positive (detectable) at screening will be excluded from the trial.

Any enrolled participant with a positive HBV DNA test result at any time must be discontinued from the study and should receive appropriate follow-up medical care, including consideration for antiviral therapy.

Study investigators should consult with a specialist physician in the care of participants with hepatitis (for example, infectious disease or hepatologist subspecialists) on whether to continue any immunosuppressant therapy including investigational product for a period of time while antiviral therapy is being initiated. Timing of withdrawal from investigational product should be based on recommendation of the consulting specialist physician in conjunction with the investigator and local or regional medical guidelines or standards of care.

Upon discontinuation from investigational product, the participant should be discontinued from the study. Any participant who discontinues the study for any reason will complete the ETV before entering the PTFU.

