- CCI every 2 weeks (Q2W) CCI
- CCI Q2W CCI

Study RHCG will be conducted in 4 parts:

- Open-label treatment (OLT) Period: 16 weeks.
- OLE Period: 88 weeks.
- LTE Period: 160 weeks.
- Post-treatment follow-up (PTFU; Visits 801, 802, and 803): 4 to 12 weeks after the last visit.

Participants who complete the OLT period may continue to the OLE period of the study. Participants who complete the OLT and OLE periods of this study may participate in an open-label LTE period.

Participants receiving adalimumab during the OLT period who did NOT attain a JIA ACR 30 response at Week 16 will be switched to ixekizumab in the OLE period. Participants receiving adalimumab during the OLT period who did attain a JIA ACR 30 response at Week 16 will be given the option to switch or not to switch to ixekizumab in the OLE period. The decision to switch for participants who achieved a JIA ACR 30 response will be left to the participant/participant's caregiver and investigator. A switch from adalimumab to ixekizumab during the OLE period may also occur at any other visit after Week 16 based on the participant/participant's caregiver and investigator's decision. After switching to ixekizumab, the participants will not have the option to resume adalimumab treatment during the remainder of the trial participation. Any adalimumab participants that complete the open label extension period of the study will be reassigned to ixekizumab starting with Treatment Period 3 (refer to Section 6.1 for additional details). Adalimumab participants who choose not to switch to ixekizumab at the end of the open label period will enter the PTFU and be considered study completers.

Participant who do not enroll in the LTE study or discontinued early (participants who have received at least 1 dose of study drug) should enter the PTFU period and complete through Visit 802. Participants may be followed beyond Visit 802 for continued monitoring of their neutrophil counts if determined by the sponsor/investigator that additional monitoring is needed. If a participant discontinues study drug early, the participant will complete the early termination visit (ETV) and then enter the PTFU period.

Study Population:

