
Notes:
 
 Due to blood volume restrictions, some laboratory tests may not be collected. Laboratory samples are recommended to be collected as described in the sponsor provided weight-based prioritization chart. If ETV occurs on the same day as the scheduled visit, any assessments/procedures conducted during the scheduled visit should not be repeated for a separate ETV. The required post-treatment follow-up visits should occur for all study participants, except for those with concurrent infections (see Section 5.1.5 for details). 								
Visit No	V67	V68	V69	Early termination	Post-Treatment Follow-Up Period (PTFU)			Notes
				ETV	V801	V802	V803	V803 is an additional follow-up based on neutrophil count (Section 5.1.5).
Study Week	W256	W260	W264	Any Week	LV (or ETV) + 4W	LV (or ETV) + 8W	LV (or ETV) + 12W	
Study Days (Approximately)	1792 ± 7d	1820 ± 7d	1848 ± 7d	Any Day	± 7d	± 7d	± 7d	
Treatment Visits	X	X						Treatment visits are intended only for the dispensation and on-site administration of ixekizumab for the participants CCI [REDACTED] who have opted for on-site administration.
Inventory 2 Short Form (CDI-2)								
Pain Numeric Rating Scale			X	X				
Morning Joint Stiffness Duration			X	X				
Parent's Global Assessment of Well-Being			X	X				To be completed by caregiver until participant is >14 years of age, at which time, the participant will complete their own questionnaires.
Laboratory Tests								
Acute phase reactant (hsCRP)			X	X				
Acute phase reactant (ESR)			X	X				To be performed locally.
Administer TB test(s) (if applicable)	TB testing required only based on clinical assessment of TB risk and according to local regulations and/or local standard of care Section 9.4.6; Appendix 2).						QuantiFERON-TB Gold, T-Spot or PPD (if applicable) (Section 9.4.6; Appendix 2) PPD to be read locally.	
HBV DNA (if applicable)			X	X			X	Positive for HBcAb requires a follow up test for HBV DNA. See Section 9.4.4 for details.
Urine pregnancy test			X	X	X	X	X	See Section 9.4.5 and Appendix 6 for details. Females only. To be performed locally.
Clinical chemistry			X	X	X	X	X	
Hematology			X	X	X	X	X	

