5.1.5. Post-Treatment Follow-Up Period

Participants who have received at least 1 dose of study drug (including those who do not enter in the LTE period or discontinued early) should enter the PTFU period for a minimum of 12 weeks after their last regularly scheduled visits (or the date of their ETV). Required study visits should occur at 4 weeks after and at 8 weeks after the last regularly scheduled visit (or the date of the participant's ETV) (Visits 801 and 802, respectively), except for participants with concurrent infections that require systemic anti-infective therapy (described below).

If, at the last scheduled visit or ETV, a participant's neutrophil count is <1500 cells/ μ L ($<1.50 \times 10^3/\mu\text{L}$ or <1.50 GI/L) and less than the participant's baseline neutrophil count, the following measures should be taken:

- Participants with concurrent infection: If there is a concurrent infection that requires systemic anti-infective therapy, the participant should receive appropriate medical care and a repeat test for neutrophil count should be performed at least Q4W (or sooner as appropriate) until resolution of infection. Upon resolution of infection, the neutrophil count should be monitored using the required study visits in the PTFU period design at Visits 801 (4 weeks after resolution of infection), 802 (8 weeks after last visit), and 803 (if necessary; 12 weeks after last visit); additional visits may be required depending on the degree of neutropenia.
- Participants without concurrent infection: If there is no concurrent infection that requires systemic anti-infective therapy, the neutrophil count should be monitored using the required study visits in the PTFU period design, Visits 801 (4 weeks post ETV or last regularly scheduled visit), 802, and 803 (if necessary); additional visits may be required depending on the degree of neutropenia.
- For Visit 801 and subsequent visits, the following monitoring applies:
 - As long as a participant's neutrophil count is <1000 cells/ μ L ($<1.00 \times 10^3/\mu\text{L}$ or <1.00 GI/L) at any follow-up visit, the participant should return for additional visits at least Q4W (unscheduled visits may be required).

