 - As long as a participant's neutrophil count is ≥1000 cells/ μ L and <1500 cells/ μ L ($\geq1.00 \times 10^3/\mu\text{L}$ and $<1.50 \times 10^3/\mu\text{L}$ or ≥1.00 GI/L and <1.50 GI/L) at any follow-up visit, the participant should return for additional visit(s) at least every 4 to 8 weeks (unscheduled visits may be required).
 - If at Visit 803 the participant's neutrophil count remains <1500 cells/ μ L ($<1.50 \times 10^3/\mu\text{L}$ or <1.50 GI/L) and less than the participant's baseline neutrophil count or if the investigator deems additional follow-up may be necessary, the investigator in consultation with Lilly or qualified designee will determine the appropriate management of the participant and the appropriate timing of additional contact(s) or visit(s).
 - If at Visit 802 or Visit 803 the participant's neutrophil count is ≥1500 cells/ μ L ($\geq1.50 \times 10^3/\mu\text{L}$ or $\geq1.50 \times 10^3/\mu\text{L}$) or greater than or equal to the

participant's baseline neutrophil count (whichever is lower), the participant's participation in the study will be considered complete unless the investigator deems additional follow-up necessary.

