9.4.4. Laboratory Tests

For each participant, laboratory tests detailed in [Appendix 2](#) should be conducted according to the Schedule of Activities (Section 2).

Blood volume restrictions are anticipated to be applicable for participants 2 to <8 years old and particularly for participants 10.0 to <20.0 kg in body weight; however, it may be used for older participants if local regulations require restrictions on blood volumes. The Blood Volume Prioritization Tool is provided in [Appendix 7](#).

Due to blood volume restrictions, some laboratory samples may not be collected (for example, cell flow cytometry in case needed to reduce blood volumes of a certain visit). Laboratory samples should be collected as described in a sponsor-provided weight-based prioritization chart.

Additional allowances to accommodate blood volume restrictions may include, but are not limited to the following:

- Blood draws for Visit 1 and Visit 2 may be divided over 2 days if the 24-hour blood volume limit is exceeded.
- Hepatitis B virus DNA will be collected as a reflex test prior to Visit 2 and is only required for participants who are positive for HBcAb.
- Hepatitis C virus RNA will be collected as a reflex test prior to Visit 2 and is only required for participants who are positive for HCV antibody.

Use of local anesthetics or devices consistent with local prescribing information is permitted during the study visit to ease discomfort associated with venipunctures. Lilly or its designee will provide the investigator with the results of laboratory tests analyzed by a central vendor, if a central vendor is used for the clinical study.

Any clinically significant findings from laboratory tests that result in a diagnosis and that occur after the participant receives the first dose of investigational product should be reported to Lilly or its designee as AE via electronic data entry.

The investigator must review the laboratory report, document this review, and record any clinically relevant changes occurring during the study in the AE section of the CRF. The laboratory reports must be filed with the source documents.

9.4.5. *Pregnancy Testing*

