6.12.4.2. Neutrophil Follow-up

The following analyses will be conducted on the Neutrophil Follow-up Population defined as patients who have an absolute neutrophil count < 1500 cells/ μL (SI units: $< 1.5 \times 10^9/L$) at the last scheduled visit or early termination visit prior to entering the follow-up period and less than the

patient's baseline neutrophil count (that is, prior to first injection at Week 0). These patients are monitored during the follow-up period until neutrophil recovery.

Neutrophil clinical recovery is defined as an absolute neutrophil count ≥ 1500 cells/ μ L (SI units: $\geq 1.5 \times 10^9/L$) or greater than or equal to a patient's minimum neutrophil count for baseline (defined as the minimum assessment recorded on or prior to the date of first study drug injection at Week 0 [Visit 2]).

If a patient's neutrophil count has not recovered, within 12 weeks after entering the follow-up period (Visit 802), the patient will return for Visit 803 (12 weeks after Visit 802). Additional visits may be required for appropriate patient management depending upon the degree of neutropenia. If at Visit 802, a patient has met the criteria for neutrophil recovery, the patient's participation in the study will be considered complete, unless the investigator deems additional follow-up may be necessary.

The number and percentage of patients achieving neutrophil clinical recovery will be presented by dosing regimen and week interval for Neutrophil Follow-Up Population for PTFU Period. The number and percentage of patients with an absolute neutrophil cell count that is at least 25%, 50%, 75%, or 100% of the patient's baseline absolute neutrophil count (that is, prior to first injection at Week 0), irrespective of absolute neutrophil minimum, will be included in the summary.

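### The HBV DNA test required 12 weeks after the last ixekizumab dose is scheduled at a conditional visit, so an HBcAb-positive participant can finish the study without it

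*Protocol*

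**What the plan says.** Section 9.4.11.2 of the protocol requires participants enrolled with a positive HBcAb and undetectable HBV DNA to be monitored "every 3 to 4 months during treatment and 12 weeks after the last dose of ixekizumab". Sections 5.1.1 and Appendix 2 (note h) send sites to the Schedule of Activities for this testing.

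Table RHCG.2.6 marks HBV DNA at Visit 69, at the early termination visit (ETV) and at Visit 803. Visits 801 and 802 are blank. Its note on the last follow-up visit reads "V803 is an additional follow-up based on neutrophil count (Section 5.1.5"). Its note on the HBV DNA row reads "Positive for HBcAb requires a follow up test for HBV DNA. See Section 9.4.4 for details". The HBV DNA text in Section 9.4.4 covers only screening: "Hepatitis B virus DNA will be collected as a reflex test prior to Visit 2".

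On follow-up visits, Section 5.1.5 says "Required study visits should occur at 4 weeks after and at 8 weeks after the last regularly scheduled visit" (or the ETV) and treats Visit 803 as something done if necessary. Once neutrophils are adequate at Visit 802 or 803, "participation in the study will be considered complete unless the investigator deems additional follow-up necessary". The Synopsis says that participants who stop early or do not enter the extension "should enter the PTFU period and complete through Visit 802".

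**The concern.** The protocol requires a safety test but schedules it at a visit that most participants have no reason to attend. The trigger for Visit 803 is a low neutrophil count, which has nothing to do with hepatitis B status. No text makes the visit mandatory for HBcAb-positive participants.

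A site that follows the visit schedule exactly could therefore discharge an HBcAb-positive participant whose last HBV DNA result dates from Visit 69 or the ETV. The post-dose test for viral reactivation would be missed. A site that looks up the rule from the table's note is sent to Section 9.4.4, which does not contain it.

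Chemistry is drawn at Visits 801 and 802 and can start the hepatic work-up in Section 9.4.11.1. That happens only after liver tests have risen, so it does not replace the DNA test.

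**Working it through.** **Is the table read correctly?** In Table RHCG.2.6 the hematology row falls at Visits 69, ETV, 801, 802 and 803, and the PK row at Visits 69, ETV and 802. The columns line up, so the HBV DNA row (69, ETV, 803) is truly blank at 801 and 802.

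**Inputs**
- Required timing: 12 weeks after the last ixekizumab dose (Section 9.4.11.2).
- Last dose in the long-term extension: Week 260, Visit 68 (Table RHCG.2.6 marks no administration at Visit 69).
- Last visit: Week 264, Visit 69.
- Visits 801, 802 and 803: last visit or ETV plus 4, 8 and 12 weeks.
- Alternative last dose: Week 264, because SAP Section 6.1.2.3 ends the extension period after an injection at Visit 69.

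**Completers of the long-term extension.** Weeks after dose = visit week − week of last dose.

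| Visit | Week | Status | HBV DNA marked | After Week 260 dose | After Week 264 dose |
|---|---|---|---|---|---|
| 69 | 264 | required | yes | 264 − 260 = 4 | 0 |
| 801 | 264 + 4 = 268 | required | no | 8 | 4 |
| 802 | 264 + 8 = 272 | required | no | 12 | 8 |
| 803 | 264 + 12 = 276 | conditional | yes | 16 | 12 |

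With a Week 260 dose, a participant who finishes at Visit 802 has a last HBV DNA test 12 − 4 = 8 weeks short of the requirement. Visit 802 falls on the required date, but no draw is marked there. Attending Visit 803 would give a test at 16 weeks.

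**Early terminators.** Let g be the weeks from last dose to ETV. The documents do not give g; I assume 0 to 4 under dosing every 4 weeks.
- ETV draw: g = 0 to 4 weeks after the dose, so 12 − g = 8 to 12 weeks short.
- Visit 802: g + 8 = 8 to 12 weeks after the dose.
- Visit 803: g + 12 = 12 to 16 weeks after the dose.

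No single visit number gives 12 weeks for everyone, so the draw has to be dated from the last dose.

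**A further inconsistency.** SAP Section 6.12.4.2 dates the last follow-up visit differently: "the patient will return for Visit 803 (12 weeks after Visit 802"). That would be Week 272 + 12 = 284, which is 284 − 260 = 24 weeks after a Week 260 dose.

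**The case against.** The strongest reply is that the test is not waived. Section 9.4.11.2 calls it required, and Section 5.1.1 and Appendix 2 (note h) say HBcAb-positive participants must be tested according to the schedule. Section 5.3 ties completion to the last visit or last scheduled procedure in that schedule. Read together, these could make the Visit 803 draw obligatory, and skipping it a protocol deviation. It is true that the requirement remains in force. But all these provisions except Section 9.4.11.2 refer back to a schedule that places the draw at a conditional visit, so they do not settle whether that visit must take place.

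Section 5.1.5 also sets a 12-week minimum for follow-up, and its completion rule sits within the instructions for low neutrophil counts. Both points are fair. However, the 12-week minimum is followed at once by a statement that names only the 4- and 8-week visits as required. And if the completion rule applies only to participants with low counts, those with adequate counts have no trigger for Visit 803 at all. Investigators may extend follow-up, but nothing directs them to do so for hepatitis B.

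The blood-volume tool in Appendix 7 has its own HBV DNA row. In the text available, its follow-up marks differ by age table: Visit 801 for 15 years and older, Visit 802 for 8 to under 15, and both for 2 to under 8. These cells may have been disturbed in extraction, and the tool is only guidance. It does not override the schedule, although the Visit 802 mark agrees with part of the fix below.

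The cross-reference error is small: the earlier extension table (Visits 30 to 42) points correctly to Section 9.4.11.2. It matters because the wrong reference is in the table that governs follow-up.

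**Conclusion.** The concern holds. The text and the schedule disagree, and a participant who follows the schedule can miss a required safety test. For extension completers the shortfall is 8 weeks if the last dose is at Week 260, as Table RHCG.2.6 shows. If the SAP's Week 264 injection is right, the Visit 69 test falls in the same week as the last dose and the shortfall is 12 weeks. For early terminators it is 8 to 12 weeks under the assumed gap of 0 to 4 weeks between last dose and ETV.

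The documents do not say how many participants are HBcAb-positive; there may be very few or none. The primary analysis is not affected. The point should be corrected because the protocol expressly admits these participants and makes the monitoring a condition of enrolling them.

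**What to change.** In Table RHCG.2.6 and Section 5.1.5:
- Require an HBV DNA draw 12 weeks after the last ixekizumab dose for every HBcAb-positive participant, regardless of neutrophil count.
- Place it at Visit 802 for extension completers last dosed at Week 260. For early terminators with a short gap between last dose and ETV, use Visit 803 or a separate draw dated from the last dose.
- Make study completion for these participants conditional on that draw.
- Point the HBV DNA note in Table RHCG.2.6 to Section 9.4.11.2.

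The cost is wording, since the test is already required. The added burden is one further visit or draw for those whose Visit 802 falls before 12 weeks.
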